### 4.3.2 ENROLLMENT/BASELINE/TREATMENT VISITS

#### **Visit 2 – Enrollment/Baseline/Treatment 1 Visit (Day 0)**

The investigator will confirm that the subject still meets the inclusion/exclusion criteria. This Baseline visit includes the first of the four treatments. In addition to the treatment, concomitant medications, photographs and the pain VAS and Tolerability Scale are to be completed by the patient. Investigator to assess immediate and short term response and complete a Modified Manchester Scar Scale (MSS) assessment.

Photographs will be taken prior to first treatment and throughout the study according to specified time points detailed in the Schedule of Events Table utilizing the Antera 3D Imaging System.

A topical anesthetic may be prescribed and applied to the treatment site prior to treatment at the investigator's discretion. The parameters may be modified during subsequent visits, as per the practitioner's discretion.

The investigator will examine the treated areas and report immediate and short term response (20-30 minutes post-treatment) using a 5-point scale. The assessment of discomfort/pain based on the subject's completion of the 10 cm VAS should also be documented immediately after each treatment.

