## 4.3 STUDY SCHEDULE

### 4.3.1 SCREENING

#### **Visit 1, Screening Visit (Day -14 to 0)**

Informed consent will be obtained from the subject prior to any study procedure, clearly indicating his/her understanding of the requirements and possible risks associated with study participation and other applicable treatment options.

Subject will be screened for eligibility to participate in the clinical study using the inclusion/exclusion criteria. During screening, the study doctor will review the subject's medical/surgical history, demographics and examine the subject's targeted area to ensure that it meets the study criteria.

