#### **Visit 3 – Treatment 2 - Week 4 (+/- 7 days)**

The Subject is to return to the clinic for their second treatment. In addition to the treatment, concomitant medications, photographs, AEs and the pain VAS and Tolerability Scale are to be completed by the patient. Investigator to assess immediate and short term response.

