### **4.3.3 FOLLOW-UP**

#### **Visit 6 – 12 Week Follow Up Post Final Treatment (+/- 7 days)**

Subjects will return to the clinic 12 weeks after the final treatment. Adverse events, and any changes to concomitant medications will be recorded. Subjects will complete a Patient Satisfaction questionnaire. Investigator to complete a Global Aesthetic Improvement Scale (GAIS) and Modified MSS assessment. Photographs of the treated area will be taken.

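### Could the baseline Modified MSS at Visit 2 be scored after the first treatment, and does the protocol need changing to prevent it?

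*Protocol*

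**What the plan says.** Section 2.1.2 of the protocol makes investigator-rated change from baseline on the Modified MSS, at 12 and 16 weeks after treatment, a secondary performance endpoint. The baseline score comes from Visit 2 (section 4.3.2), of which the protocol says: "This Baseline visit includes the first of the four treatments". The instruction there is: "Investigator to assess immediate and short term response and complete a Modified Manchester Scar Scale (MSS) assessment".

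The same visit gives timing for other items. For images: "Photographs will be taken prior to first treatment", and then "according to specified time points detailed in the Schedule of Events Table". For the treatment response, the investigator is to "report immediate and short term response (20-30 minutes post-treatment) using a 5-point scale". The pain VAS is to be documented straight after each treatment. No timing is attached to the Modified MSS.

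At screening (section 4.3.1) the doctor examines the "targeted area to ensure that it meets the study criteria", and no scar score is listed. At Visit 3 the instruction reads only "Investigator to assess immediate and short term response", and Visits 4 and 5 say the same. The scale returns at Visit 6: "Investigator to complete a Global Aesthetic Improvement Scale (GAIS) and Modified MSS assessment". It is listed again at Visit 7.

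**The concern.** The baseline score and the first treatment fall on the same day, and the scale shares a sentence with a reading taken after treatment. At Visits 3 to 5 the response instruction stands alone, so at Visit 2 the scale looks like an addition to a post-treatment task. An investigator who completed both forms together 20-30 minutes after treatment would break no explicit instruction in the visit text.

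The stake is a one-sided bias. The device is used in ablation or coagulation mode with multiple passes (section 4.1.2), and the protocol expects an immediate response worth grading. If that reaction worsened the baseline score, its resolution by 12 to 16 weeks would look like benefit. No control group is described that would share the error, the investigator alone rates this endpoint, and the visit text lists no second pre-treatment score to fall back on. An analysis plan could define baseline, but it could not recover a score that was never taken.

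**Working it through.** The protocol states no significance level, power, effect size or standard deviation, so there is no figure of its own to reproduce. The check is mainly one of reading.

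**Step 1. Where the scale is scored.**

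| Visit | Modified MSS listed? | Timing relative to that day's treatment |
|---|---|---|
| 1, screening | No | n/a |
| 2, baseline and treatment 1 | Yes | Not stated |
| 3, 4, 5, treatments 2 to 4 | No | n/a |
| 6, 12 weeks after final treatment | Yes | No treatment that day |
| 7, 16 weeks after final treatment | Yes | No treatment that day |

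There is one score before follow-up and there are two at follow-up. Visit 2 is the only source of a baseline in the visit text.

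**Step 2. Does sharing a sentence imply shared timing?** The preceding sentence of Visit 2 lists photographs beside the pain VAS and the Tolerability Scale. The photographs are expressly taken before the first treatment and the VAS immediately after it. That list therefore mixes items from both sides of treatment, so grouping in this paragraph says nothing about order.

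**Step 3. What does the protocol place after treatment?** The closing paragraph of Visit 2 names the 5-point response and the VAS. It does not name the Modified MSS. If anything, this points to a score before treatment.

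**Step 4. What is the score for?** The visit is labelled baseline, and section 2.1.2 measures change from baseline. A score taken after the intervention is not a baseline in ordinary use.

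**Step 5. Can the bias be sized?** Only by assuming every input that matters. Take the 15 treated subjects of section 3.1, no true change, and (assumed) a paired two-sided 5% t-test, counting only results in the direction of improvement. With 14 degrees of freedom the critical value is 2.145. A mean baseline shift of d standard deviations of the change gives noncentrality d × √15, and the false-improvement rate is the upper tail of the noncentral t distribution beyond 2.145:

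| d (assumed) | d × √15 | Rate |
|---|---|---|
| 0 | 0 | 2.5% |
| 0.1 | 0.387 | 5.5% |
| 0.25 | 0.968 | 14.5% |
| 0.5 | 1.936 | 43.8% |
| 1 | 3.873 | 94.9% |

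Here d is averaged over all subjects, so the last two rows need late scoring to be routine, or a very large shift in those scored late. If instead each subject has an assumed 50% chance of late scoring, with an assumed 1-point shift when it happens, simulation gives about 21%, 14% and 9% at assumed standard deviations of 1.5, 2 and 3 points. With a 25% chance it gives about 8%, 6% and 5%. The whole range, from no inflation to near certainty, is set by the assumptions. The protocol favours no row except through its evident intention to score before treatment, which is the first.

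**The case for a change.** The strongest case for a change is that the protocol fixes the order for photographs, VAS and 5-point response but not for this scale. The error would favour the device, an analysis plan could not repair it afterwards, and the remedy would be one sentence with no added procedure.

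The facts in that case stand. The order is unstated, the score is the only one before follow-up, and a late score is not expressly excluded in the text at hand. The likely direction of bias is plausible too, although the documents give no item content for the scale and no acute-reaction data to confirm it.

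The step from silence to defect does not stand. The protocol nowhere directs or suggests post-treatment scoring once the paragraph is read as a list of procedures. Order within a visit is commonly settled in the schedule of assessments or the case report form. Visit 2 cites the Schedule of Events Table for photographs only, so the table cannot be counted on to cover the scale, but it cannot be ruled out either. That the remedy would be cheap does not show that there is an error to correct.

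**Conclusion.** No change to the plan follows. This is a gap in within-visit order that a sensible investigator fills correctly by scoring the scars before treating them.

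If late scoring did occur, its reach would be limited to the investigator-rated Modified MSS, one of two secondary performance endpoints. The Antera volumetric and photographic GAIS primary endpoints use images whose baseline set is fixed before the first treatment. The amount of bias is unknown and cannot be bounded usefully from the protocol.

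The conclusion rests on two assumptions: that baseline carries its ordinary meaning for the site, and that the Schedule of Events Table, not in the text at hand, does not place the Visit 2 score after treatment. If the table did so, it would conflict with the endpoint definition in section 2.1.2 and the point would have to be reopened.

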#### **Visit 3 – Treatment 2 - Week 4 (+/- 7 days)**

The Subject is to return to the clinic for their second treatment. In addition to the treatment, concomitant medications, photographs, AEs and the pain VAS and Tolerability Scale are to be completed by the patient. Investigator to assess immediate and short term response.

#### **Visit 4 – Treatment 3 - Week 8 (+/- 7 days)**

The Subject is to return to the clinic for the third treatment. In addition to the treatment, concomitant medications, photographs, AEs and the pain VAS and Tolerability Scale are to be completed by the patient. Investigator to assess immediate and short term response.

#### **Visit 5 – Treatment 4 - Week 12 (+/- 7 days)**

The Subject is to return to the clinic for the fourth and final treatment. In addition to the treatment, concomitant medications, photographs, AEs and the pain VAS and Tolerability Scale are to be completed by the patient. Investigator to assess immediate and short term response.

### **4.3.3 FOLLOW-UP**

#### **Visit 6 – 12 Week Follow Up Post Final Treatment (+/- 7 days)**

Subjects will return to the clinic 12 weeks after the final treatment. Adverse events, and any changes to concomitant medications will be recorded. Subjects will complete a Patient Satisfaction questionnaire. Investigator to complete a Global Aesthetic Improvement Scale (GAIS) and Modified MSS assessment. Photographs of the treated area will be taken.

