##### **2.1.3 SAFETY ENDPOINTS**

- Subject's assessment of discomfort and pain after treatments as measured by a 10 cm visual analog scale (VAS) and Tolerability Scale
- Subjects experiencing a treatment-related adverse event (AE) by 16 weeks post-treatment.

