### 3 STUDY ENROLLMENT AND WITHDRAWAL

#### 3.1 STUDY POPULATION

The study will enroll male and female adult subjects requesting fractional radiofrequency treatment of stretch marks until 15 subjects have been treated according to the study protocol.

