## 4 INVESTIGATIONAL DEVICE

### 4.1 INVESTIGATIONAL DEVICE AND CONTROL DESCRIPTION

#### 4.1.2 DEVICE SPECIFIC CONSIDERATIONS

- Device model(s): Venus Viva™
- Device settings and programming: Ablation or Coagulation Mode; 180-280 volts, 5-30 ms pulse duration
- Duration of exposure and frequency: Multiple passes, 4 treatments, roughly 4-6 weeks apart, multiple treatment areas per subject may be treated. Treatment area size – 3"x3" or smaller

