#### **Visit 7 – 16 Week Follow Up Post Final Treatment (+/- 7 days)**

Subjects will return to the clinic for a final study visit 16 weeks after the final treatment. Adverse events, and any changes to concomitant medications will be recorded. Subjects will complete a Patient Satisfaction questionnaire. Investigator to complete a GAIS and Modified MSS assessment.

Photographs of the treated area will be taken.

The termination form will be completed, and subjects will be terminated from the study. The PI will record all reportable events with start dates occurring any time after informed consent is obtained until 7 (for non-serious AEs) or 30 days (for SAEs) after the last day of study participation.

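### Adverse events after the fourth treatment are first asked about at 12 weeks, against about 4 weeks after the first three, so short-lived reactions to the last treatment may be under-ascertained

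*Protocol*

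**What the plan says.** Section 2.1.3 of the Protocol defines the AE safety endpoint per subject: "Subjects experiencing a treatment-related adverse event (AE) by 16 weeks post-treatment". Section 3.1 sets the size of the single group: enrolment continues "until 15 subjects have been treated according to the study protocol".

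Section 4.3.2 places Treatments 2, 3 and 4 at Weeks 4, 8 and 12, each within 7 days either way, and lists AEs among the items at each of these visits (Visits 3, 4 and 5). Section 4.1.2 describes the spacing more loosely: "4 treatments, roughly 4-6 weeks apart". At every treatment visit, including the last, the investigator also assesses immediate and short-term response. The Visit 2 text times this at 20 to 30 minutes after treatment.

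Section 4.3.3 then moves directly from the last treatment to Visit 6: "Subjects will return to the clinic 12 weeks after the final treatment", again within 7 days either way. AEs are recorded there and at Visit 7, 16 weeks after the last treatment. At Visit 7 "subjects will be terminated from the study", yet the same section requires events to be recorded "until 7 (for non-serious AEs) or 30 days (for SAEs) after the last day of study participation".

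**The concern.** The endpoint counts any treatment-related AE up to 16 weeks after treatment, but the chance that an event is recorded depends partly on when the subject is next asked. The first three treatments share one recall interval and the fourth has a much longer one. A mild skin reaction that appears some days after the session and clears within weeks is past the same-day check and over before Visit 6. It is recorded only if the subject reports it unprompted or still remembers it about three months later.

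Two features of the design give this some weight. With 15 subjects, each missed subject moves the proportion by 1/15 = 6.7 percentage points. The Visit 2 text also lets the practitioner change device parameters at later visits, so AEs seen after the earlier sessions do not fully stand in for those after the last one. No later analysis can recover an event that nobody asked about in time.

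**Working it through.** **Intervals to the next AE enquiry.** Inputs are the visit weeks and 7-day windows in sections 4.3.2 and 4.3.3.

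| Treatment | Next AE enquiry | Nominal days | With windows |
|---|---|---|---|
| 1 (Day 0) | Visit 3 | 28 | 21 to 35 |
| 2 (Week 4) | Visit 4 | 28 | 14 to 42 |
| 3 (Week 8) | Visit 5 | 28 | 14 to 42 |
| 4 (Week 12) | Visit 6 | 84 | 77 to 91 |

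Treatment 1 carries one window (28 ± 7). For Treatments 2 and 3 both ends can move (28 ± 14). Visit 6 is counted from the final treatment itself (84 ± 7). The nominal ratio is 84/28 = 3. With the 6-week end of the spacing in section 4.1.2 it is 84/42 = 2. The ranges do not overlap: the longest interval after an earlier treatment is 42 days and the shortest after Treatment 4 is 77.

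**Effect on the endpoint.** The Protocol gives no AE rate and no capture rate, so everything here is assumed: AE risk per treatment p = 0.10, independent across treatments; capture at a 4-week enquiry 0.95; capture at 12 weeks q = 0.3, 0.5 or 0.8.

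- All four treatments asked about at 4 weeks: 1 − (1 − 0.10 × 0.95)^4 = 1 − 0.905^4 = 32.9%.
- As scheduled: 1 − 0.905^3 × (1 − 0.10q).

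| q | Recorded share | Shortfall in subjects of 15 | Treatment 4 events lost, 1 − q/0.95 |
|---|---|---|---|
| 0.3 | 28.1% | 0.72 | 68% |
| 0.5 | 29.6% | 0.50 | 47% |
| 0.8 | 31.8% | 0.17 | 16% |

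**Sensitivity to the assumed risk.** With full capture after Treatments 1 to 3 and half of Treatment 4 events captured, compare 1 − (1 − p)^4 with 1 − (1 − p)^3 × (1 − 0.5p):

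- p = 0.10: 34.4% against 30.7%, 0.55 of 15 subjects.
- p = 0.20: 59.0% against 53.9%, 0.77 of 15.
- p = 0.40: 87.0% against 82.7%, 0.65 of 15.

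If no Treatment 4 event were captured, the shortfall would be about 1.1 to 1.5 subjects. If all were captured it would be zero.

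**The period after Visit 7.** Visit 7 falls on day 112 ± 7, that is 105 to 119 days after Treatment 4, and the endpoint closes at 16 weeks, day 112. If Visit 7 is on day 112 or later, the whole 7-day or 30-day period lies outside the endpoint. If it is on day 105, at most 112 − 105 = 7 days fall inside.

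**The case against.** The strongest reply is that nothing here is misstated. The follow-up visits match the 12- and 16-week endpoints, Visit 6 does record AEs, spontaneous reports are not excluded, and same-day reactions to Treatment 4 are seen in clinic. A subject who had a treatment-related AE after any earlier session is already counted. If AEs cluster within subjects, the shortfall is smaller than the independence model gives. All of this stands. It limits the concern to transient reactions that begin after the same-day check, in subjects not already counted, but does not remove it.

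A reader might be tempted to go further in four ways that the document does not support.

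- *The endpoint is undercounted.* This is not shown. The capture rates are assumptions, and the document supports only that under-ascertainment is possible.
- *The last treatment will falsely look the best tolerated.* No endpoint compares AEs between treatments, and the pain VAS and Tolerability Scale are completed at every treatment visit, including the fourth. The 16 to 68% loss in the working concerns Treatment 4 events, whereas the endpoint counts subjects.
- *The 7/30-day period after Visit 7 lowers the safety endpoint.* It lies outside the 16-week cut-off, apart from up to 7 days when Visit 7 is early.
- *Subjects have no contact at all after Visit 7, so that period cannot be observed.* The text describes no contact, but the Schedule of Events Table mentioned under Visit 2 is not in the text available. The rule also sets a duty to record, which unsolicited reports can partly meet.

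**Conclusion.** The point holds as a modest weakness in how AEs are ascertained. After Treatment 4 the first described enquiry comes two to three times as late as after Treatments 1 to 3, and nothing described between the same-day check and Visit 6 would pick up a short-lived reaction. Such reactions may therefore be under-ascertained in the section 2.1.3 endpoint. The size is not derivable from the Protocol. With the assumed 10% risk and 30 to 80% capture at 12 weeks, the loss is 0.17 to 0.72 of a subject, under one in 15. It exceeds one only in the extreme case where no Treatment 4 event is captured. This is a worthwhile low-cost improvement and not a threat to the study's conclusions.

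The period after Visit 7 is a separate minor point. Section 4.3.3 ends participation at that visit and also requires later events to be recorded, without describing how they would come to the site's attention.

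**What to change.** Add to section 4.3.3 one scripted AE query by telephone or e-mail, made by existing site staff about 4 weeks after Treatment 4, so that the recall interval matches that after Treatments 1 to 3. It needs no clinic visit and changes neither treatment nor the efficacy assessments. The cost is one short contact for each of 15 subjects. The reported AE rate may rise slightly because more of the real events are captured.

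Separately, reconcile the two statements under Visit 7: either describe how events in the 7-day and 30-day periods will be found, or make the recording period and the end of participation agree. The choice belongs to the investigator and sponsor under the reporting rules that apply to them. At most it adds one further short contact per subject.

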#### **Visit 7 – 16 Week Follow Up Post Final Treatment (+/- 7 days)**

Subjects will return to the clinic for a final study visit 16 weeks after the final treatment. Adverse events, and any changes to concomitant medications will be recorded. Subjects will complete a Patient Satisfaction questionnaire. Investigator to complete a GAIS and Modified MSS assessment.

Photographs of the treated area will be taken.

The termination form will be completed, and subjects will be terminated from the study. The PI will record all reportable events with start dates occurring any time after informed consent is obtained until 7 (for non-serious AEs) or 30 days (for SAEs) after the last day of study participation.

## **5 ETHICS/PROTECTION OF HUMAN SUBJECTS**

### **5.1 ETHICAL STANDARD**

The investigator will ensure that this study is conducted in full conformity with the latest version of the Declaration of Helsinki (2013), ISO 14155:2011 and any other applicable country's ethical policy statement.

## 5.2 INFORMED CONSENT PROCESS

### 5.2.1 CONSENT/ASSENT AND OTHER INFORMATIONAL DOCUMENTS PROVIDED TO PARTICIPANTS

Informed consent is required for all subjects in a study. In obtaining and documenting informed consent, the investigator should comply with applicable regulatory requirements and should adhere to ISO 14155:2011 and to the latest version of the Declaration of Helsinki (2013).

### 5.2.2 CONSENT PROCEDURES AND DOCUMENTATION

Participants will have the opportunity to carefully review the written consent form and ask questions prior to signing. The participant will sign the informed consent document prior to any procedures being done specifically for the study. The participants may withdraw consent at any time throughout the course of the trial. A copy of the informed consent document will be given to the participants for their records. The rights and welfare of the participants will be protected by emphasizing to them that the quality of their medical care will not be adversely affected if they decline to participate in this study.

## 5.3 PARTICIPANT AND DATA CONFIDENTIALITY

The study protocol, documentation, data, and all other information generated will be held in strict confidence by the participating investigators, their staff, and their agents.

Study participant research data, which is for purposes of statistical analysis and scientific reporting, will be transmitted to and stored at the Investigator's office. Individual participants and their research data will be identified by a unique study identification number. At the end of the study, all study databases will be de-identified and archived by the investigator.
